10.5.8.3.2. Serious, Unexpected Adverse Drug Reactions

All ADRs that are both serious and unexpected are subject to expedited reporting to regulatory agencies. An unexpected ADR is one for which the nature or severity is not consistent with information in the relevant source documents.

The following documents or circumstances will be used to determine whether an AE/ADR is expected:

1. For a medicinal product not yet approved for marketing in a country, the RSI of the company's IB will serve as the source document in that country.
2. Reports that add significant information on specificity or severity of a known, already documented serious ADR constitute unexpected events. For example, an event more specific or more severe than described in the RSI of the IB would be considered "unexpected."

10.5.9. Pregnancy

If at any point any pregnancy test is confirmed positive, the subject will be withdrawn from the study treatment.

Details of all pregnancies in female subjects and female partners of male subjects will be collected after the start of study treatment and until 30 days after the last dose.

Pregnancy (during maternal or paternal exposure to study treatment) does not meet the definition of an AE; however, to fulfill regulatory requirements, any pregnancy and/or pregnancy outcome should be reported via the Pregnancy Report Form to the designated Sponsor Contact **within 24 hours of awareness.**

Abnormal pregnancy outcomes (eg, spontaneous abortion, fetal death, stillbirth, congenital anomalies, ectopic pregnancy) are considered SAEs and should be reported as such even if outside the SAE reporting period.

10.6. Procedures for Overdose

See the IB for additional information.

There is no established overdose threshold for this clinical study, nor is there any recommended specific treatment for an overdose but to provide supportive care if clinically indicated.

In the event of a suspected overdose, the investigator and/or treating physician should:

1. Closely monitor the subject for any AE/SAE and laboratory abnormalities and provide supportive care.

2. Contact the medical monitor immediately.
3. Obtain a plasma sample for PK analysis within 7 days from the date of the last dose of study treatment, if possible, and if requested by the medical monitor.
4. Document the total quantity of the excess dose, taking into consideration the duration of the overdose in the eCRF and the time frame.

Subjects who overdose will be counseled on correct dosing and administration of study treatment. Decisions regarding study discontinuation, dose interruptions, or dose modifications will be made by the investigator in consultation with the medical monitor based on the clinical evaluation of the subject.

[REDACTED]

[REDACTED]

[REDACTED]

[REDACTED]

[REDACTED]

[REDACTED]

[REDACTED]

[REDACTED]

[REDACTED]

[REDACTED]

[REDACTED]

[REDACTED]

[REDACTED]

11. PLANNED STATISTICAL METHODS

11.1. General Considerations

Statistical considerations will be discussed in Sections 11.2 to 11.8 for the Double-Blind Treatment Period, and in Section 11.9 for the Open-Label Extension Period. Details regarding the statistical analyses will be provided in the SAP, which will be finalized prior to database lock of the Double-Blind portion of the study.

Continuous variables will be summarized using the number of observations, mean, standard deviation (SD), median, minimum, and maximum. Categorical variables will be summarized using frequency counts and percentages.

11.2. Determination of Sample Size

It is assumed that the percent change in EASI from Baseline to Week 12 will be normally distributed with a SD of 41%. Assuming a 1:1:1 randomization, 120 subjects (40 subjects each in 1 mg etrasimod, 2 mg etrasimod, or placebo groups) is sufficient to achieve at least 90% power to detect a difference of 35% in EASI from Baseline to Week 12 between each of the etrasimod treatment groups and placebo by a 2-sample t-test using a 1-sided significance level of 0.025 with estimated SD at 41%. This sample size also accounts for an estimated drop-out rate up to 25%.

11.3. Analysis Sets

For purposes of analysis, the following analysis sets are defined (Table 7).

Table 7: Analysis Sets

Analysis Set	Description
Full Analysis Set (FAS)	The FAS includes all randomized subjects, irrespective of whether they received any study treatment.
Modified Full Analysis Set (mFAS)	The mFAS population consists of all randomized subjects who received at least 1 dose of study treatment, have a baseline measurement, and have at least 1 post-randomization measurement. The mFAS is endpoint specific, therefore subjects included in the analysis set for 1 endpoint may differ from another endpoint, based on the baseline and post-baseline data.
Per Protocol Set	The Per Protocol Set consists of all subjects in the FAS population who adhere to the protocol. The Per Protocol Set will be used in sensitivity analyses of the primary and key secondary endpoints to evaluate the influence of major protocol violators and protocol deviators on the primary results. Subjects may be excluded from this population if they violate the eligibility criteria or significantly deviate from the study plan. Specific reasons for warranting exclusion from this population will be documented prior to database lock and may include, but are not limited to, study treatment noncompliance, receiving incorrect study treatment, missing more than a defined number of visits while still on study,

Analysis Set	Description
	and chronic prohibited medication use while on study treatment. The statistical analysis plan, which will be finalized prior to database lock, will be the final documentation for the Per Protocol Set definition.
Safety Set	The Safety Set includes all randomized subjects who received at least 1 dose of study treatment.
[REDACTED]	[REDACTED]

11.4. Missing Data

11.4.1. Primary Methods of Handling Missing Data and Rescue Medication Uses

In order to analyze primary and secondary efficacy endpoints at Week 12 in the Full Analysis Set (FAS), handling missing data and rescue medication uses are specified as following.

For the primary endpoint of percentage change in EASI from Baseline to Week 12, EASI scores after rescue medication use will be set to missing. All missing EASI scores at scheduled visits up to Week 12 will be imputed using a multiple imputation (MI) technique with a fully conditional specification method and predictive mean matching for EASI scores (Heitjan 1991, van Buuren 2007). Detailed MI model descriptions and analysis procedures will be specified in the SAP.

For analysis of dichotomous endpoints (eg, 75% reduction in EASI [EASI-75], vIGA 0 to 1) at Week 12, all subjects in the FAS will be included in the analyses. Subjects in any of the following cases will be considered as “non-responders” or “failure”:

- Use rescue medications during treatment;
- Prematurely discontinue from study due to any reason prior to Week 12; or
- With missing data at Week 12 for any reason.

11.4.2. Sensitivity Analyses

In addition to the primary methods for handling missing data and rescue medication use in the FAS described in Section 11.4.1, the following sensitivity analyses will be performed for the primary and key secondary endpoints using alternative methods to handle missing data and rescue medication use, and/or in alternative analysis populations:

- For the MI analysis of percentage of change in EASI from Baseline to Week 12, data missing at random within each treatment group will be investigated using tipping point analysis method ([REDACTED]).
- Percentage of change in EASI from Baseline to Week 12 will be analyzed in the modified Full Analysis Set (mFAS), data will be set to missing after rescue medication uses; all missing data will be imputed using post-baseline last observation carried forward method.

- Percentage of change in EASI from Baseline to Week 12 will be analyzed in the mFAS set, data will be set to missing after rescue medication uses; all missing data will be imputed using post-baseline worst-case-carry-forward method.
- Proportion of subjects achieved EASI-75 response at Week 12 will be analyzed in the mFAS set using EASI scores imputed by the MI method discussed in Section 11.4.1.
- Observed data analyses in mFAS set, regardless of rescue medication uses and without missing data imputation:
 - For longitudinal continuous variables (eg, percentage of change in EASI from Baseline to Week 12), mixed effects model with repeated measures (MMRM) analysis will be performed and by visit results will be reported;
 - For longitudinal dichotomous measures (eg, EASI-75, vIGA 0 to 1), logistic regression analysis will be performed by visit.
- Completers analyses of primary and secondary endpoints for subjects who complete 12 weeks of study treatment.
- Analyses of primary and key secondary endpoints in the Per Protocol set.

11.5. Efficacy Analyses

The primary endpoint of percentage change in EASI from Baseline to Week 12 will be analyzed in the FAS and using MI procedure with analysis of covariance (ANCOVA) model. The ANCOVA model will include treatment group as factor, Baseline EASI score and randomization factor as covariates. Multiple results of ANCOVA (least square [LS] means and LS mean difference from placebo) for each MI dataset will be analyzed and reported along with 95% confidence interval (CI) and p-value using Rubin's method (██████████).

Proportion-based key secondary endpoints (eg, EASI-75, vIGA 0 to 1) at Week 12 will be analyzed in the FAS using the Cochran-Mantel-Haenszel method adjusted for randomization stratification factor. The number and percentage of subjects achieving the goal and the difference in proportion between treatment groups achieving the goal, along with p-value and the 95% CIs will be reported.

Other secondary endpoints (listed in Section 11.5.4) will be analyzed using the following methods in general and specific details will be discussed in the SAP.

- Longitudinal continuous variables measured at scheduled visits up to Week 12 will be analyzed using a MMRM model. The MMRM model will include treatment group, visit, and interaction of treatment-by-visit as factors, and baseline measure and randomization stratification factor as covariates. An unstructured covariance matrix will be specified for the MMRM model. LS means at visit and LS mean differences between treatment group with p-values and corresponding 95% CIs will be reported. This method will also be applied to other score based or continuous measures.
- Longitudinal dichotomous measures at scheduled visits will be analyzed using a logistic regression model. The model will include treatment group as a factor, Baseline EASI score and randomization stratification factor as covariates. The odds ratios and 95% CIs, and associated p-value will be reported.

Analysis methods for exploratory endpoints will be described in the SAP.

In addition to between group analyses on the primary and secondary endpoints, dose response of key efficacy measures for the 2 etrasimod doses and placebo will be assessed as exploratory using appropriate analysis models, which will be specified in the SAP.

Efficacy data will be analyzed by randomized treatment, while safety data will be analyzed by actual treatment.

11.5.1. Endpoint Definitions

Efficacy will be assessed by changes in AD severity using EASI, vIGA, SCORAD, and BSA. Symptoms of itch will be assessed using the pruritus NRS. Patient-reported outcomes will also be assessed using the DLQI, POEM, and PGA.

The following definitions will be used to assess efficacy outcomes:

11.5.2. Primary Efficacy Endpoint

- Percent change in EASI from Baseline to Week 12.

11.5.3. Key Secondary Efficacy Endpoints

- Proportion of subjects achieving EASI-75, defined as a 75% reduction of EASI from Baseline to Week 12.
- Proportion of subjects with a vIGA 0 to 1 (on a 5-point scale) score and a reduction from Baseline of ≥ 2 points at Week 12.

11.5.4. Secondary Efficacy Endpoints

- Percent change in peak pruritus NRS from an itch daily diary from Baseline to Week 12.
- Proportion of subjects with improvement (reduction) in peak pruritus NRS ≥ 3 from an itch daily diary from Baseline to Week 12.
- Proportion of subjects achieving EASI-50, defined as a $\geq 50\%$ reduction of EASI from Baseline to Week 12.
- Proportion of subjects achieving EASI-90, defined as a $\geq 90\%$ reduction of EASI from Baseline to Week 12.
- Change and percentage change in percent BSA AD involvement from Baseline to Week 12.

11.5.5. Exploratory Efficacy Endpoints

- Change in DLQI from Baseline to Week 12.
- Change in POEM from Baseline to Week 12.
- Percent change in SCORAD from Baseline to Week 12.

█ [REDACTED]

█ [REDACTED]

█ [REDACTED]

11.5.6. Efficacy assessment during open-label extension:

These efficacy outcomes will be measured at scheduled visits up to 52 weeks: EASI, vIGA, SCORAD, BSA, Pruritus NRS, POEM, DLQI, and PGA. Dichotomous response outcomes derived from specific scores will be assessed.

█ [REDACTED]

█ [REDACTED]

█ [REDACTED]

█ [REDACTED]

█ [REDACTED]

11.5.8. Subgroup Analyses

- Sex (male, female)
- Race (white, non-white)
- Age (\leq or $>$ median)
- Baseline vIGA (3 or 4)
- Baseline EASI score (\leq or $>$ median)
- Baseline percent BSA AD involvement (\leq or $>$ median)

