 CMH=Cochran-Mantel-Haenszel; NRS= Numerical Rating Scale; BSA=Body Surface Area; ANCOVA=Analysis of Covariance; MMRM=Mixed Model with Repeated Measures.

F. OLE Period Efficacy Analysis

The following endpoints will be assessed in the OLE Period:

- Continuous variables: observed value and change (percent) from Baseline in EASI, SCORAD, BSA, pruritus NRS, POEM, DLQI, and PGA
- Dichotomous variables: EASI-75, vIGA

The above variables will be summarized by visit using descriptive statistics based on the applicable analysis set, with following considerations:

- Only observed cases will be used with no imputation of missing data
- Summaries will be provided for 1 treatment group (“Total”) in OLE Period and also by original treatment groups (“Etrasimod 1mg”, “Etrasimod 2mg” and “Placebo”) in DB Treatment Period
- Change from baseline in continuous variables will be analyzed on change from DB baseline and change from OLE baseline, respectively

For OLE Period, subgroup analyses of main efficacy outcomes (EASI, vIGA, NRS, BSA) will be performed in the following categories:

- Week 12 EASI-75 responders versus non-responders
- Week 12 vIGA responders versus non-responders
- EASI score at DB baseline (\leq or $>$ median)
- Percent BSA AD involvement at DB baseline (\leq or $>$ median)

G. Efficacy Analysis on Subgroups of Subjects

Subgroup analyses of primary and key secondary endpoints for the DB Treatment Period will be conducted for each of the following groups:

- Sex (male, female)
- Race (White, Other)
- Age (\leq or $>$ median)
- Baseline vIGA (3 or 4)
- Baseline EASI score (\leq or $>$ median)
- Baseline percent BSA AD involvement (\leq or $>$ median)

9. Safety Analyses

Safety analyses will use data from the SAF for DB Treatment Period and OLE Safety Set for OLE Period. For the DB Treatment Period, summary will be done on the 3 treatment groups; for the OLE Period, summary will be done on 1 treatment group in the OLE Period and 3 subgroups in the DB Treatment Period. Week 16 is the last

scheduled visit in DB Treatment Period and first scheduled visit in OLE Period. Overall (DB + OLE) summaries will be provided as detailed below.

A. Exposure and Compliance

The following exposure and compliance parameters will be defined and summarized for DB treatment and OLE Periods separately, and for overall using descriptive statistics:

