Additional sensitivity analysis for percent change in EASI will be performed with observed cases in the FAS using the MMRM model described in [section 8 \(subsection B\)](#)

D. Additional Subgroup Analyses for EASI-75 and vIGA

Prior Systemic Failure Subject (Yes, No)

Prior Systemic Failure Subject are subjects who previously had ineffective/intolerant therapy in oral steroid, oral JAK and Dupilumab, or other conventional Systemic therapy:

- 15 subjects in the 2mg etrasimod group: 

- 3 subjects in the 1mg etrasimod group: 

- 10 subjects in the placebo group: 

EASI-75 and vIGA response rate by visit will be analyzed for the subgroups of Prior Systemic Failure Subject (Yes, No) and using the same CMH analysis described in [section 8 \(subsection C\)](#).

13. References

Carpenter, J. R. and Kenward, M. G. (2013), *Multiple Imputation and Its Application*, New York: John Wiley & Sons.

Ruberg SJ. Dose Response Studies. II. Analysis and Interpretation. *J Biopharm Stat* 5(1), 15-42 (1995).

van Buuren S. Multiple imputation of discrete and continuous data by fully conditional specification. *Stat Methods Med Res.* 2007;16(3):219-242.

Appendix 1

B. Summary of Plasma Concentrations

Concentrations below the limit of quantification (BLQ) will be assigned a numerical value of zero for the calculation of descriptive statistics and plotting of concentrations. For geometric mean and geometric %CV, the zero values will be excluded.

Individual subject etrasimod plasma concentrations will be presented in the data listings (showing treatment received, sex, age, scheduled nominal time, and actual time) and also summarized using descriptive statistics (n, mean, SD, % Coefficient of Variance [CV], geometric mean, geometric %CV, minimum, median, and maximum) for each scheduled visit, as following:

- For timepoints in the DB Treatment Period (Baseline/Day 1 to Week 16), by actual treatment received in DB Treatment Period
- For timepoints in OLE Period (Week 16 to Week 72), by actual treatment received in DB Treatment Period and overall

Mean (SD) plasma concentrations will be plotted versus scheduled nominal time from start of treatment on both linear and semilogarithmic scales according to the above summaries.

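### The subgroup plan cuts age, baseline EASI and baseline BSA at the median and includes no treatment-by-factor interaction estimate, so it does not directly measure whether the effect varies

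*Protocol*

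**What the plan says.** Protocol 11.5.8 is a bare list of six factors: sex, race, age, baseline vIGA, baseline EASI score and "Baseline percent BSA AD involvement". Sex, race and vIGA are natural categories. Age, EASI and BSA are divided at or below versus above the median. The protocol gives no method.

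SAP 8.G repeats the list under one sentence: "Subgroup analyses of primary and key secondary endpoints for the DB Treatment Period will be conducted for each of the following groups". It mentions no interaction term, between-level contrast or continuous-modifier analysis.

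The SAP names a subgroup method in one other place, section 12.D, for a post hoc factor. There EASI-75 and vIGA response "will be analyzed for the subgroups of Prior Systemic Failure Subject (Yes, No) and using the same CMH analysis" as for the main comparison. The analyses that would be inherited (SAP 8.B and 8.C) report p-values as well as estimates and confidence intervals.

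Protocol 11.6 and SAP 5.F describe the pairwise comparisons as exploratory, without Type I error control. Baseline EASI enters the primary ANCOVA as a covariate (protocol 11.5, SAP 8.B), but not in a term with treatment.

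**The concern.** A subgroup analysis is there to show whether the treatment effect varies. If the main analysis is simply repeated in each level, the reader gets two smaller-sample results per factor and dose and will tend to compare their p-values. That comparison is not a test of difference. With roughly half the sample in each level, the two results will often fall on opposite sides of the significance line when the effect is identical in both.

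Cutting a measured factor at its median also discards the ordering within each half, so a real trend with severity or age is estimated less precisely than the data allow. In Phase 2, both problems could steer the choice of population for the next study.

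**Working it through.** **Inputs** (protocol 11.2, repeated in SAP 4.C)
- Effect and power: "at least 90% power to detect a difference of 35% in EASI from Baseline to Week 12".
- Test level: "using a 1-sided significance level of 0.025".
- Variability: percent change in EASI "will be normally distributed with a SD of 41" percent.
- Size: "Assuming a 1:1:1 randomization, 120 subjects (40 subjects each in 1 mg etrasimod, 2 mg etrasimod, or placebo groups").
- Dropout: "This sample size also accounts for an estimated drop-out rate up to 25" percent.

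**Step 1: reproduce the plan's figure.** The exact two-sample t-test (noncentral t) with difference 35 and SD 41 has power 89.2% at 29 per arm and 90.2% at 30. Then 30 / 0.75 = 40 per arm, 120 in all. The stated sample size is reproduced.

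**Step 2: power within one half.** Assume a 50:50 split and the same 35-point effect in both halves. SE = 41 × √(2/n), with n per arm per half.

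| | n = 20 (all 40 per arm count) | n = 15 (25% lost) |
|---|---|---|
| SE within a half | 13.0 | 15.0 |
| Power p | 74.9% | 61.7% |
| One half significant, the other not, 2p(1 − p) | 2 × 0.749 × 0.251 = 37.6% | 2 × 0.617 × 0.383 = 47.3% |
| SE of the difference between halves, √2 × SE | 18.3 | 21.2 |
| 95% half-width of that difference, 1.96 × SE | 35.9 | 41.5 (42.4 with a t quantile) |

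The primary analysis imputes missing EASI in the FAS, so the effective size lies between the two columns.

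**Step 3: across factors.** The six splits reuse the same subjects, so the per-factor figures cannot be multiplied. A simulation with three arms, a shared placebo group, six 50:50 factors and a uniform 35-point effect (2,500 trials per scenario) gave:
- one dose, at least one discordant factor of six: about 70-83%;
- one dose, at least one of the three median-cut factors: about 59-73%;
- both doses, at least one of 12 comparisons: about 87-95%.

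Each range covers 40 and 30 per arm, and zero or 0.6 correlation among three of the factors. The correlation made little difference.

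**Step 4: a direct interaction test.** With no true interaction it is significant in 5% of cases per factor, and in 1 − 0.95⁶ = 26.5% for any of six independent factors. It remains weak: 80% power with the median split needs a gap between halves of (1.96 + 0.84) × SE, about 51 points (SE 18.3) to 59 points (SE 21.2).

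**Step 5: cost of the median cut.** For a linear interaction, the information kept is the squared correlation between the factor and its above-median indicator. For a normal factor this is 2/π = 0.637, a loss of 36%. The loss is 25% for a uniform factor and 52% for an exponential one. The documents give no distributions. Illustrative shapes respecting the entry limits gave 32% (age), 35% (EASI) and 43% (BSA).

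For a normal factor the continuous term carries 1/0.637 = 1.57 times the information. Power for a 35-point gap between halves rises from about 48% to 67% at n = 20, and from about 38% to 54% at n = 15.

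EASI-75 and vIGA were not computed, because the documents give no response rates.

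**The case against.** Several objections stand in whole or part.

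- **The method is not stated.** A reader might infer that the plan prescribes a separate test in each half, with its own p-value. Neither list says so. Separate estimation is inferred from SAP 12.D, which concerns a different factor, and the table shells are not available. The inference is fair but remains one. The median cut and the absence of any interaction estimate, by contrast, are plain on the page.
- **A single subgroup does not usually mislead.** It is tempting to say that a uniform effect will usually look uneven. For one factor and one dose the chance is 38-47%, below one half. It exceeds one half only across the set of factors.
- **Half fits only three factors.** The splits for sex, race and vIGA are unknown. Uneven splits raise discordance, however: at 30 evaluable per arm, 70:30 gives 55% and 80:20 gives 65%; at 40 per arm, 49% and 62%.
- **The information loss is specific.** It concerns a linear interaction and depends on the factor's shape. The prognostic use of baseline EASI as an ANCOVA covariate is unaffected.
- **The comparisons are exploratory, and confidence intervals allow an approximate contrast.** For the continuous endpoint a reader could derive the between-level difference from two separate intervals. This limits the consequence, but it leaves the reader to calculate what the plan should report.
- **The fix gains modest power.** Interaction intervals would be about as wide as the planned effect, and six unadjusted tests still give a false signal in about 27% of trials. Showing that width is itself useful, because it tells readers how little these subgroups can establish.

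**Conclusion.** The point holds as a cheap improvement to an exploratory analysis. The plan cuts three measured factors at the median and provides no treatment-by-factor interaction estimate.

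If the main analyses are repeated by level, as seems intended, a uniform 35-point effect gives a significant/non-significant split in about 38-47% of single factor-and-dose comparisons. For one dose, at least one of six factors shows such a split in about 70-83% of trials. The interaction test gives 5% per factor and about 27% for any of six. The median cut costs about 36% of the information on a linear interaction for a normal factor, and 25-52% across the shapes tried.

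These figures rest on the plan's 35-point effect and SD of 41, on 50:50 splits, on 15 to 20 subjects per arm per level, on no precision gain from covariates, and on the primary endpoint only. A reader might infer that the trial's main result is at risk. The documents do not support that: the primary analysis is untouched.

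**What to change.** In SAP 8.G and protocol 11.5.8:

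1. For each factor, fit one model in the whole FAS with a treatment-by-factor interaction: the primary ANCOVA for percent change in EASI; logistic regression, or the difference between subgroup risk differences, for EASI-75 and vIGA response.
2. Enter age, baseline EASI and baseline BSA as continuous in the interaction term.
3. Report the interaction estimate with its 95% CI, labelled exploratory.
4. Show within-level estimates and CIs, including the median-split ones, as description without p-values.
5. State that precision is low: the 95% half-width for a difference between halves is about 36 to 42 points, as large as the planned effect.

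The cost is SAP and protocol wording and a few extra model runs on data already collected; no visits or subjects are added. The one small downside is that the continuous term assumes a roughly linear trend, which the median-split display can help check.
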